9.4.3 Handling of missing values/censoring/discontinuations

Missing data will be handled with the likelihood method with the assumption that they are MAR in the primary analyses.

9.4.4 Sensitivity analyses

In order to explore the robustness of the MAR assumption on the primary analysis, a sensitivity analysis will be carried out which assesses the situation where the data are missing not at random (MNAR); In particular, the sensitivity analysis will assume that LCZ696 patients who discontinue due to adverse events, death or lack of efficacy will not have adhered to therapy if they had stayed in the study.

A controlled multiple imputation approach based on pattern mixture models will be applied ([Carpenter and Kenward 2013](#)), whereby all missing data of patients in the LCZ696 group who permanently discontinue study treatment due to: adverse events, death or lack of efficacy, will be assumed to behave like patients in the control group (individualized medical therapy) after permanent discontinuation and will be imputed based on the data from patients in the control group (individualized medical therapy) according to the stratum (defined by prior ACEi/ARB medication usage [ACEi, ARB, None]).

All other missing data will be considered as MAR within each arm and will be imputed using a multiple imputation approach ([Carpenter and Kenward 2013](#)) based on observed data within each arm according to the stratum. Of note, patients who permanently discontinue study treatment, are not considered discontinued from the study. It is planned to continue to collect and use data at scheduled visits even after permanent discontinuation of study treatment.

Furthermore, the missing data patterns in the change from baseline in log(NT-proBNP) and the change from baseline in 6MWD will be explored via by-treatment-group box plots for patients who permanently discontinue from study treatment due to adverse events, death or lack of efficacy, for patients who permanently discontinue from study treatment due to any other reasons, for patients who did not permanently discontinue from study treatment, and for patients who take open label LCZ696 after permanent discontinuation from study treatment.

As additional supportive analyses, the primary analyses for the primary variables (the change from baseline in log[NT-proBNP] at Week 12, and the change from baseline in 6MWD at Week 24) described in [Section 9.4.1](#) will be performed for the following data as applicable:

- Data where the 6MWD after the death were set to missing for patients who died.
- Data where the last observation carry forward (LOCF) approach was performed for missing data.
- Data where the responses after the first dose of open-label RASi or open-label LCZ696 after permanent discontinuation of the study treatment will be set to missing and considered MAR. (This is called on-treatment analysis.)

The FAS will be used for the above analyses.

9.5 Analysis of secondary variables

9.5.1 Efficacy variables

All secondary efficacy variables will be analyzed using the FAS, unless otherwise specified.

9.5.1.1 KCCQ clinical summary score change from baseline

For patients who have died, the KCCQ CSS after the death will be imputed as zero. For patients who permanently discontinue study treatment, values collected after permanent discontinuation will generally be included in the analysis.

The changes from baseline in KCCQ CSS will be analyzed using a MMRM model, in which, the response variable will be the changes from baseline in KCCQ clinical summary score; stratum (defined by prior ACEi/ARB medication usage [ACEi, ARB, None]), region, treatment (LCZ696, individualized medical therapy), visit and treatment-by-visit interaction will be included as fixed-effect factors; baseline KCCQ clinical summary score (BCSS), baseline systolic blood pressure (BSBP), stratum-by-BCSS, stratum-by-BSBP, and visit-by-BCSS interactions will be included as covariates; the within-patient covariance will be modeled using an unstructured covariance matrix (a common matrix for the two treatment groups). If the model fitting procedure does not converge, the AR(1) covariance structure will be used. The analysis will include all post-baseline scheduled visits up to Week 24 (Week 4, Week 12, Week 16 and Week 24) and will be performed based on the likelihood method with an assumption of MAR for missing data (other than due to death).

Based on the MMRM model, the secondary null hypothesis, H_3 , will be tested (if applicable) based on the testing strategy, the estimates and the two-sided 95% confidence intervals will be provided for the adjusted means for the change from baseline in KCCQ CSS at Week 24 in each of the two treatment groups (LCZ696 and individualized medical therapy), and for the adjusted mean difference (LCZ696 minus individualized medical therapy) at Week 24.

In addition, the improvement and the deterioration in KCCQ CSS will be analyzed separately using longitudinal binary logistic regression models, in which, the response variables will be, accordingly, the KCCQ CSS improvement (event defined by at least 5-points improvement in KCCQ CSS) and the KCCQ CSS deterioration (event defined by at least 5-points deterioration in KCCQ clinical summary score); stratum (defined by prior ACEi/ARB medication usage [ACEi, ARB, None]), region, treatment (LCZ696, individualized medical therapy), visit and treatment-by-visit interaction will be included as fixed-effect factors; BCSS, BSBP, stratum-by-BCSS, stratum-by-BSBP and visit-by-BCSS interactions will be included as covariates; patient-specific intercepts will be included as random effects. The analysis will include all post-baseline scheduled visits up to Week 24 (Week 4, Week 12, Week 16 and Week 24) and will be performed based on the likelihood method with an assumption of MAR for missing data (other than due to death).

Based on the longitudinal binary logistic regression models, the estimates and the two-sided 95% confidence intervals will be provided for the adjusted odds ratios (LCZ696 over individualized medical therapy) at Week 24.

Besides, the KCCQ clinical summary score and the change from baseline in KCCQ CSS summary score will be summarized by visit and treatment group using n , mean, standard

deviation, min, Q1, median, Q3 max; the improvement and the deterioration in KCCQ CSS of at least 5-points will be summarized by visit and treatment group using frequencies and percentages.

The FAS will be used for the above analyses.

9.5.1.2 KCCQ overall summary score change from baseline

As an exploratory analysis, the same analyses as KCCQ CSS will also be performed for KCCQ OSS, except that the baseline KCCQ CSS in the models will be replaced by baseline KCCQ OSS.

The FAS will be used for the above analyses.

9.5.1.3 NYHA class change

The NYHA class change is a three-category ordinal variable with levels: “improved”, “unchanged”, and “worsened”, defined by at least one class improvement, no change, at least one class worsening, in NYHA class, respectively. For patients who died, the NYHA class change after the death will be categorized into “worsened”. For patients who permanently discontinue study treatment, values collected after permanent discontinuation will generally be included in the analysis.

The NYHA class change will be analyzed using a longitudinal proportional cumulative odds model, in which, the response variable will be the NYHA class change (order defined by “improved” < “unchanged” < “worsened”); stratum (defined by prior ACEi/ARB medication usage [ACEi, ARB, None]), region, treatment (LCZ696, individualized medical therapy), visit, treatment-by-visit interaction, baseline NYHA class, stratum-by-baseline and visit-by-baseline interactions will be included as fixed-effect factors; BSBP and stratum-by-BSBP interaction will be included as covariates; patient-specific intercepts will be included as random effects. The analysis will include all post-baseline scheduled visits up to Week 24 (Week 2, Week 4, Week 8, Week 12, Week 16, Week 20 and Week 24) and will be performed based on the likelihood method with an assumption of MAR for missing data (other than due to death).

Based on the longitudinal proportional cumulative odds model, the secondary null hypothesis, H_4 , will be tested (if applicable) based on the testing strategy, the estimate and the two-sided 95% confidence interval will be provided for the adjusted odds ratio (LCZ696 over individualized medical therapy) at Week 24.

In addition, the improvement and deterioration in NYHA class will be analyzed separately using longitudinal binary logistic regression models, in which, the response variables will be, accordingly, the NYHA class improvement (event defined by NYHA class change of level “improved”) and the NYHA class deterioration (event defined by NYHA class change of level “worsened”); stratum (defined by prior ACEi/ARB medication usage [ACEi, ARB, None]), region, treatment (LCZ696, individualized medical therapy), visit, treatment-by-visit interaction, baseline NYHA class, stratum-by-baseline and visit-by-baseline interactions will be included as fixed-effect factors; BSBP and stratum-by-BSBP interaction will be included as covariates; patient-specific intercepts will be included as random effects. The analysis will include all post-baseline scheduled visits up to Week 24 (Week 2, Week 4, Week 8, Week 12,

Week 16, Week 20 and Week 24) and will be performed based on the likelihood method with an assumption of MAR for missing data (other than due to death).

Based on the longitudinal binary logistic regression models, the estimates and the two-sided 95% confidence intervals will be provided for the adjusted odds ratios (LCZ696 over individualized medical therapy) at Week 24.

Besides, the NYHA class and the NYHA class change will be summarized by visit and treatment group using frequencies and percentages.

The FAS will be used for the above analyses.

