3.1 Study design

This study is a 24-week, randomized, double-blind, multi-center, parallel group, active controlled study to evaluate LCZ696 compared to individualized medical therapy on NT-proBNP, exercise capacity, symptoms and QoL in patients with HF and preserved left ventricular ejection fraction (LVEF > 40%) (Figure 3-1). Patients will be initially stratified into one of three strata according to prior treatment for comorbidities: ACEi, ARB or no RASi. Patients will then be randomized 1:1 to receive either LCZ or comparator. Patients in the ACEi strata will be randomized to receive either LCZ696 or enalapril. Patients in the ARB strata will be randomized to receive either LCZ696 or valsartan, and patients in the no RASi strata will be randomized to receive either LCZ696 or placebo. Patients in the ACEi and ARB strata must have a history of HTN. There will be no designated proportion of patients in each strata, the strata will populate based upon the patient's prior treatment regimen.

A screening epoch of up to 2 weeks will be used to assess eligibility. Patients on appropriate therapy for comorbidities will be eligible for the study. Patients will be required to have been on stable doses of baseline medications for at least four weeks prior to randomization. After randomization, patients will begin a 1 to 4 week study drug up-titration epoch followed by a 20 to 23 week maintenance epoch (Figure 3-1). Visits to assess safety and efficacy are scheduled at 4 to 6 week intervals during the maintenance epoch. The assessment to address the primary objective of reduction in NT-proBNP will be performed using data up to Week 12, and the primary objective of change in 6MWD and all secondary objectives will be performed using data up to Week 24. No interim analysis (IA) is planned.

[figure not shown]
[figure not shown]

Figure 3-1 Study design

ACEi = angiotensin converting enzyme inhibitor
 ARB = angiotensin receptor blocker
 RASi = renin angiotensin system inhibitors
 * Patients in the ACEi and ARB strata must have a history of HTN

Screening epoch

At screening (Visit 1), patients will sign the informed consent and be assessed for eligibility for study participation through review of study inclusion/exclusion criteria. Patients enrolled in the study will continue their baseline medication regimen and enter a screening epoch of up to 2 weeks in order to allow adequate time for the completion of all qualifying screening and eligibility evaluations.

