- With both H_1 and H_2 rejected at the initial step, if H_3 is rejected at one-sided 0.025, the alpha will be propagated to H_4 , such that, H_4 will be tested at full alpha (one-sided 0.025). Otherwise, the testing procedure will stop.

Figure 9-1 provides graphical illustration of the sequentially rejective testing procedure.

Figure 9-1 Graphical illustration of the sequentially rejective testing procedure

Based on the above testing procedure, if applicable, H₁, H₂ and H₃ will be tested based on the corresponding MMRM models (Section 9.4.2, Section 9.5.1.1), H₄ will be tested based on the longitudinal proportional cumulative odds model (Section 9.5.1.3)

If statistical significance had been established in the mean difference in change from baseline to Week 24 for KCCQ CSS, the following responders will be analyzed accordingly, based on the longitudinal binary logistic regression models (Section 9.5.1.1), to further illustrate the clinical relevance of the observed differences in terms of proportion of responders.

- KCCQ CSS improvement (defined by at least 5 points improvement);
- KCCQ CSS deterioration (defined by at least 5 points deterioration);

No multiplicity adjustment will be done for these supportive responder analyses (i.e., the tests for the responder analyses will be performed at nominal level of one-sided 0.025).

NT-proBNP analyses

The changes from baseline in log(NT-proBNP) will be analyzed using a mixed model for repeated measures (MMRM), in which, the response variable will be the changes from baseline in log(NT-proBNP); stratum (defined by prior ACEi/ARB medication usage [ACEi, ARB, None]), region, treatment (LCZ696, individualized medical therapy), visit and treatment-by-visit interaction will be included as fixed-effect factors; baseline log(NT-proBNP), stratum-by-baseline and visit-by-baseline interactions will be included as covariates; the within-patient covariance will be modeled using an unstructured covariance matrix (a common matrix for the two treatment groups). The analysis will include all post-baseline scheduled visits up to Week 12 (Week 4, Week 12) and will be performed based on the likelihood method with an assumption of missing at random (MAR) for missing data (Siddiqui et al 2009, National Research Council 2010).

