9.8 Sample size calculation

The sample size (2500 randomized patients) has been chosen in order to provide adequate power to evaluate both primary and secondary endpoints.

With an alpha of one-sided 0.0225, the power for the NT-proBNP will range from 92% to more than 99%, to detect a relative reduction ranging from 11% to 24% in change from baseline to Week 12 in NT-proBNP, assuming a standard deviation of 0.81 for change from baseline in the

log-transformed NT-proBNP (based on PARAMOUNT-HF data of patients with baseline KCCQ CSS < 75) and an overall drop-out rate of 10%.

With an alpha of one-sided 0.0025, the power for the 6MWD will range from 90% to 99%, to detect a mean difference ranging from 22 meters to 30 meters in change from baseline to Week 24 in 6MWD, assuming a standard deviation of 120 meters (Ingle et al 2005), an overall drop-out rate of 10%, and an overall proportion of 88% for patients with B6MWD ranging from 100 meters to 450 meters.

With an alpha of one-sided 0.0225, the power for the KCCQ CSS will range from 87% to 99%, to detect a mean difference ranging from 2 points to 3 points in change from baseline to Week 24 in KCCQ CSS, assuming a standard deviation of 15.52 points for change from baseline in the KCCQ CSS (based on PARAMOUNT-HF data of patients with baseline KCCQ CSS < 75) and an overall drop-out rate of 5%.

All alpha levels in the following sample size calculations will be one-sided 0.025.

This sample size of 2500 randomized patients aims to provide a power of approximately 90%, with the one-sided alpha level of 0.025, to demonstrate a 5% responder advantage in at least 5-point deterioration for patients who are treated with LCZ696 over individualized medical therapy when assuming the proportion of patients with at least 5-point deterioration from baseline to Week 24 in the individualized medical therapy group is 20% (based on PARAMOUNT-HF data of patients with baseline KCCQ CSS < 75) and an overall 5% dropouts.

With the same assumption of the dropout rate, this sample size will also provide a power of 69% to detect a 5% responder advantage in at least 5-points improvement in the KCCQ clinical summary score for patients who are treated with LCZ696 over individualized medical therapy when assuming the proportion of patients with at least 5-points improvement from baseline to Week 24 in the individualized medical therapy group is 55% (based on PARAMOUNT-HF data of patients with baseline KCCQ CSS < 75).

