The sensitivity of power for at least 5-points deterioration in the KCCQ clinical summary score to changes in assumptions is outlined in Table 9-1.

Table 9-1 Sensitivity of power for at least 5-points deterioration in KCCQ clinical summary score to changes in assumptions for N = 2500

Assumed probability of at least 5-points deterioration			Power for at least 5-points deterioration (one-sided alpha = 0.025)			
Individualized medical therapy	LCZ696	Difference	With 5% drop-out rate	With 10% drop-out rate	With 15% drop-out rate	With 20% drop-out rate
20%	15%	-5%	90%	88%	86%	84%
35%	30%	-5%	74%	72%	69%	67%

The sensitivity of power for at least 5-points improvement in the KCCQ CSS to changes is outlined in Table 9-2.

Table 9-2 Sensitivity of power for at least 5-points improvement in KCCQ clinical summary score to changes in assumptions for N = 2500

Assumed probability of at least 5-points improvement			Power for at least 5-points improvement (one-sided alpha = 0.025)			
Individualized medical therapy	LCZ696	Difference	With 5% drop-out rate	With 10% drop-out rate	With 15% drop-out rate	With 20% drop-out rate
55%	60%	5%	69%	67%	65%	62%
41%	46%	5%	69%	67%	64%	62%

The assumed dropout rates (Table 9-1 and Table 9-2) are for the purpose of power sensitivity analysis. During the conduct of the study, all efforts will be made to reduce missing data.

For other secondary endpoints, this sample size will provide adequate powers for reasonable effect size assumptions: power of 90% for NYHA class change, assuming 14% of the patients in the comparator and 19% of the patients in the LCZ696 group are improved in NYHA class change, 6% of the patients in the comparator and 5% of the patients in the LCZ696 group are worsened in NYHA class change (based on Week 24 PARAMOUNT-HF data of patients with baseline KCCQ CSS < 75); and power of approximately 90% to detect a between treatment group mean difference of 1.4 points or more in change from baseline in SF-36 physical component summary score, assuming a standard deviation of 10-points (Edelmann et al 2013).

East 6.3 was used for the sample size calculations.

10 Ethical considerations

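### The H4 NYHA model leaves out baseline KCCQ CSS; adding it would be a cheap, optional efficiency gain, and the stated power does not depend on it

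*Protocol*

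**What the plan says.** Protocol 9.5.1.3 and SAP 2.6.2 specify the same H4 model. The fixed factors are RASi stratum, region, treatment, visit, treatment-by-visit, baseline NYHA class, and the stratum-by-baseline and visit-by-baseline interactions. For the rest, "BSBP and stratum-by-BSBP interaction will be included as covariates; patient-specific intercepts will be included as random effects". The separate NYHA improvement and deterioration logistic models have the same terms.

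Baseline CSS (BCSS) appears as a covariate only in the KCCQ CSS models, including the random-intercept responder models of Protocol 9.5.1.1 and SAP 2.6.1.1. It is available almost without gaps. A Visit 1 CSS below 75 is an entry criterion (Protocol 4.1), KCCQ is repeated at Visit 101 (Table 6-1), and SAP 2.1.1 falls back to the last value up to randomization if the Visit 101 value is missing.

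Protocol 9.8 gives "power of 90% for NYHA class change, assuming 14% of the patients in the comparator and 19% of the patients in the LCZ696 group" as the improved proportions, and "6% of the patients in the comparator and 5% of the patients in the LCZ696 group are worsened in NYHA class change". This sits under the statement "All alpha levels in the following sample size calculations will be one-sided 0.025". Neither document says why BCSS is absent from the NYHA models.

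**The concern.** Entry requires NYHA class II to IV at Visit 1, so baseline class takes few values and cannot separate patients within a class. CSS covers much the same ground, symptoms and physical function, on a 0–100 scale. It could plausibly indicate which patients within a class are closer to moving up or down. If so, including it would sharpen the treatment comparison without extra patients or visits and, when pre-specified, without type I error cost.

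H4 is the last hypothesis in the testing chain. If H2 is rejected and H1 is not, H4 is tested at one-sided 0.0025, where power is lowest and a small gain is worth most.

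**Working it through.** **Inputs**
- "The sample size (2500 randomized patients) has been chosen in order to provide adequate power" (Protocol 9.8) and "Patients will then be randomized 1:1 to receive either LCZ or comparator" (Protocol 3.1): 1250 per arm.
- Improved / unchanged / worsened: 14 / 80 / 6% on comparator and 19 / 76 / 5% on LCZ696 (unchanged by subtraction).
- Drop-out: none is stated for NYHA. The KCCQ deterioration calculation assumes "and an overall 5% dropouts"; here 0%, 5% and 10% are shown.
- Alpha for H4: one-sided 0.025, or 0.0025 when H2 is rejected but H1 is not (Protocol 9.4.2).
- Share R² of latent NYHA-change variance that CSS explains beyond the existing covariates: not in the documents. Assumed range 0% to 10%.

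**1. The plan's 90%**

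For a tie-corrected Wilcoxon test on three categories:
- P(LCZ696 better) = 0.19 × 0.86 + 0.76 × 0.06 = 0.2090
- P(comparator better) = 0.14 × 0.81 + 0.80 × 0.05 = 0.1534
- Effect θ = (0.2090 − 0.1534)/2 = 0.0278
- Pooled proportions 0.165, 0.780, 0.055; sum of cubes 0.4792
- Var(θ) = (1 − 0.4792)/12 × 2/n per arm

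At 5% drop-out (n = 1187.5), SE = 0.00855, Z = 0.0278/0.00855 = 3.25, and power = Φ(3.25 − 1.96) = 90.2%. With no drop-out it is 91.6%; with 10%, 88.6%. The stated 90% reproduces with no covariate contribution. At alpha 0.0025 and 5% drop-out, power = Φ(3.25 − 2.807) = 67.2%.

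**2. Effect of adding CSS**

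Start from exactly 90%: Z = 1.960 + 1.282 = 3.242. Scale by 1/√(1 − R²), so power = Φ(3.242/√(1 − R²) − z), with z = 1.960 or 2.807. The patient equivalent is 2500 × R².

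| Assumed R² | Power at 0.025 | Power at 0.0025 | Equivalent patients |
|---|---|---|---|
| 0% | 90.0% | 66.8% | 0 |
| 1% | 90.3% | 67.4% | 25 |
| 2% | 90.6% | 68.0% | 50 |
| 5% | 91.4% | 69.8% | 125 |
| 10% | 92.7% | 72.9% | 250 |

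**3. Checks on the scaling**

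- *Seven-visit random-intercept cumulative odds model* (48 runs per R², intercept SD 2.0 assumed, constant treatment effect). The SE of the treatment log odds ratio fell by 1.2%, 3.4% and 7.1% at R² of 2%, 5% and 10%.
- *Single-visit proportional odds model without random intercepts* (1500 runs per R²). The SE did not fall (0.1003 to 0.1008 at R² = 5%). The log odds ratio moved away from zero instead, and mean Z rose by 0.7%, 1.7% and 3.5%.

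At R² = 10% the Z multipliers are 1.035 (single visit), 1/√0.9 = 1.054 (scaling) and 1/0.929 = 1.076 (seven visits, SE change alone). The scaling lies between the two models, and all agree on direction.

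**4. Weight of the 0.0025 path**

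H4 is tested at 0.0025 only if H1 fails at 0.0225. Protocol 9.8 gives H1 at least 92% power, so on the plan's own assumptions the path arises in at most 8% of trials. The largest gain there, 72.9 − 66.8 = 6.1 points, is worth at most 6.1 × 0.08 = 0.49 point overall.

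**The case against.** The strongest reply is that nothing is wrong. The secondary models follow a visible convention: each adjusts for its own endpoint's baseline plus systolic blood pressure. H4 does exactly that and has about 90% power under its own assumptions. No passage gives an association between baseline CSS and later NYHA change, still less one conditional on baseline class. The entry limit of 75 also narrows the CSS range, so the gain may be close to zero. H4 is reached only after H2 and H3 are rejected, and the 0.0025 path is rare.

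All of that stands, and it sets the size and priority of the point. It does not show a material downside to adding the covariate. The convention is also not limited to own-endpoint baselines, because blood pressure already enters as a covariate from another domain.

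A reader might infer more than the documents support:
- That the model adjusts only for baseline NYHA class and blood pressure. It also adjusts for stratum, region and several interactions.
- That precision is demonstrably being given away. This depends on an association the documents do not report.
- That H4 is underpowered. The 90% reproduces without CSS.

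**Conclusion.** This is an optional efficiency improvement of low priority. BCSS is absent from the H4 model and both NYHA logistic models although it exists for essentially every randomized patient.

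For an assumed R² of 0% to 10%, the gain from a 90% base at one-sided 0.025 is 0 to about 2.7 percentage points; on the 0.0025 path it is 0 to about 6 points. These figures rest on the assumed R², on 5% drop-out borrowed from the KCCQ calculation as the match to 90%, and on a variance-scaling approximation. The direction is supported by a seven-visit random-intercept simulation of modest size.

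**What to change.** Before unblinding, in Protocol 9.5.1.3 and SAP 2.6.2:
- Add BCSS, with the efficacy-baseline definition of SAP 2.1.1, as a continuous main effect in the H4 cumulative odds model. For consistency, add it to the NYHA improvement and deterioration models.
- Give BCSS a named place in the SAP 2.1.1 non-convergence removal order, for example immediately before BSBP. Make clear that baseline in that list means baseline NYHA class for these models.
- Add BCSS to the NYHA imputation models in SAP 2.6.4, so that they contain the covariates of the analysis model.
- Describe the reported odds ratio as conditional on BCSS as well as the other covariates.
- If only the SAP is changed, record it in SAP Section 4, which currently states no change from protocol.

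The cost is one more model term, a few lines of text and code, and an odds ratio conditional on one more baseline variable. No new data or derivation is needed. If CSS proves uninformative, one extra main effect in a trial of 2500 costs practically nothing.
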